- In-person MTM (required only of pharmacists randomized to MTM + PGx testing arm): The purpose of this CE is to review elements of MTM, development of medication action plans, and incorporation of PGx testing into an MTM session. The development of this module was adapted from the MTM module offered by the American Pharmacists' Association (APhA). Attendance may be waived if the pharmacist provides proof of completion of the APhA MTM CE program.

PART II. PHARMACOGENETIC TESTING IN COMMUNITY PHARMACY TRIAL

Part II of the study will involve the cluster randomized trial to compare the effect of PGx testing as a stand-alone service to PGx testing with MTM (Figure 1/Aim 2)). We aim to enroll 20 pharmacist (in 20 separate pharmacies) and 360 patients in the study (~18 per pharmacy).

PGx Testing. Testing will be available for patients with active prescriptions for the drugs listed in Table 1. The drugs were selected based on CPIC guidelines and/or drug labels with PGx information that are likely to be filled at community pharmacies. If new CPIC guidelines are developed by the start of the study, we will update the list accordingly. Testing for each of the genes listed in the table will be provided by the CLIA-certified laboratory Pathway Genomics (CLIA # 05D1092505; San Diego, CA). The test for this study is a customized panel test that includes CYP2D6, CYP2C19, CYP2C9, SLC01B1 and VKORC1/CYP2C9. Currently, turnaround time for testing is 7-10 days. Given the varying coverage policies for PGx testing, all test fees will be supported by the study.

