and can read and write in English, and have a new or existing prescription (<1 year active) for a drug listed in Table 1 to be eligible to participate. Each pharmacy will identify existing patients eligible for testing through a query of their database for active prescriptions for the selected drugs. If more than 30 patients in a pharmacy are identified by the database search, we will ask pharmacists to contact patients with the newest prescriptions. Patients will be contacted by phone or in-person by the pharmacist to introduce the study. Interested patients will be asked to visit the pharmacy to learn more about testing, sign the consent form requested by the testing laboratory, and provide a DNA sample (buccal swab). Patients who have had PGx testing for one of the genes in Table 1 or had an MTM within the past 12 months will be ineligible. All women and minorities who meet the study inclusion criteria will be eligible to participate in the study. Based on our power calculations, we estimate that we would need to enroll 18 patients per cluster (360 total).

Patients who consent to testing based on their pharmacist's recommendation will be asked to provide a buccal swab for DNA extraction. Patient samples will be sent for testing to Pathway Genomics laboratory. Testing will be provided at no cost for participants. As the Pathway Genomics' clinical tests are currently available to any clinician, only the consent required by the testing lab will be required of the patient.

Patients in the control arms will be identified by each participating pharmacy; two controls will be identified per each participant in the PGx arms (2:1) and matched on drug, age and gender. Time on treatment, medication changes (dose/drug selection), and refill history (adherence) data will be collected along with demographic data and compared to patients in the PGx testing arms. Based on their pharmacy records, patients who have undergone MTM or PGx testing outside of the study will be excluded from the control arm.

Risk/Benefit Assessment. If patients decide to have pharmacogenetic testing, a buccal swab sample is required. There are no known risks to a buccal swab sample. The sample, or DNA extracted from the sample, will be sent to the laboratory and stored only for the time necessary laboratory regulations.

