The integration of PGx testing into the community pharmacy setting will be assessed primarily through surveys of patients and pharmacists. In addition, we will conduct semi-structured interviews with a subset of pharmacists to gather more in-depth understanding of their experiences, perceived barriers, and likelihood to continue to offer PGx testing. The measures to be assessed are described below; clinical outcome measures will be collected about the medications impacted by PGx only.

Patient Surveys (Aim 2b) The baseline survey will collect demographic data, prior knowledge about PGx, self-reported co-medications, time on treatment for PGx-related drug(s), and medication adherence (see Table 2; Appendix 5). The follow-up survey will gather data on 1) satisfaction with the testing experience in a pharmacy setting, including use/provision of patient materials from Aim 1; 2) perceived value of testing; and 3) comprehension of test result. Additional measures include medication-taking behaviors and information-sharing. The follow-up survey will be administered approximately one month after the PGx results are communicated since many of the medications are prescribed in 90-day allotments. Key survey questions are further described below; data on age, gender, co-medications, and time on treatment for PGx-related drug(s) will also be collected for controls.

- [Baseline] Literacy. We will screen for health literacy using the validated single question: “How confident are you filling out forms by yourself?” Compared to the gold standard literacy tools REALM or S-TOFHLA, this single question accurately predicts inadequate health literacy⁹⁹ and is more feasible to administer.
- [Follow-up] Comprehension of Results. Our primary outcome will be comprehension of test results based on gist recall of the phenotype.¹⁰⁰ Specifically, the outcome of interest is the patient’s recognition of the presence or absence of a variant gene. Due to the complexity of genotypes and presumed patient unfamiliarity with gene nomenclature, we do not believe it reasonable to expect patients to recall their genotype. Therefore, we will instead ask patients to circle their specific metabolizer status (e.g., rapid, extensive, intermediate, poor, or inconclusive). For the genes *SLCO1B1* and *VKORC1*, we will ask patients to indicate their test

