report found that they carried a known variant allele or not. We and others have used this approach to assess patient comprehension of genetic test results.^{101,102} The primary endpoint for comprehension is dichotomous (correct/incorrect). To assess patients' understanding of the significance of the result to their care, we will ask if the pharmacist recommended any changes to their treatment based on test result. Responses will be compared to the test results reported in the pharmacist's patient log (see below) and recommended pharmacist changes.

- **[Follow-up] Satisfaction with Testing Experience.** To assess patients' perceived value and satisfaction with PGx testing, we will ask about their likelihood to have PGx testing again in the community pharmacy setting. A survey tool from Walker et al.¹⁰³ will be adapted to gain further information about participant satisfaction. These questions have scale outcomes and will be treated as continuous variables.
- **[Follow-up] Perceived Value of Testing.** We will assess the perceived impact of the PGx test result on patients' confidence in the safety and effectiveness of the prescribed drug. A PGx result may be perceived as 'good' or 'favorable' if it is believed to inform selection of a safe drug or dosage adjustment. However, some patients may perceive the result as less than favorable if they are found to be a poor metabolizer and a lower dose is needed to reduce risk of side effects. Such patients may feel that the lower dose will be ineffective, and potentially fail to adhere to the drug regimen. In addition, we will assess participants' likelihood to pay for future PGx testing as a surrogate measure for perceived value.

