Patient Study Population. Patients will be invited to complete two surveys: 1) a baseline survey after they consent to testing and 2) a follow-up survey after they receive the test results. A brochure will be provided to the patient that will describe the purpose of the survey, risks and benefits, participant rights, investigator contact information, and how to access the survey. The pharmacist can ask if the patient would be willing to be contacted by the study coordinator or to complete the survey on their own time online. Upon completion of the baseline survey, participants will be asked to indicate if they would be interested in participating in the follow-up survey and re-contacted.

Pharmacist Study Population. Participating pharmacists will be invited to complete the baseline survey prior to the start of the in-person training session. The instructor (the clinical pharmacist on the research team) will describe the purpose of the survey, risks and benefits, participant rights, investigator contact information, and how to access the survey online (paper copy will also be available upon request). For the post-study interviews, pharmacists will be contacted at the completion of the study to ascertain interest to be interviewed.

Survey Administration. We will use Redcap, an online survey tool to design and administer the surveys. Redcap offers features that allow for custom designs, branching/skip logic, randomization of answer choices, multiple collection features and data output formats. A customized link will be sent to each participant to access the survey set, enabling the study coordinator to track and link responses between survey sets and to send reminders to only those who do not respond. Paper or phone option will be made available as requested; pharmacies can elect which method they prefer at the start of the study.

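### The primary comprehension outcome sits in a follow-up survey whose only described entry is through a voluntary baseline survey, and the 18 per cluster is an enrolment count with no stated response allowance

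*Combined protocol and SAP*

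**What the plan says.** All places are in the combined protocol and SAP.

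- **Primary outcome.** Part III, Patient Surveys: "Our primary outcome will be comprehension of test results based on gist recall of the phenotype". The item is marked as a follow-up item and scored correct or incorrect. Table 2 lists it first in the follow-up survey, which is given about one month after results are communicated.
- **Consent.** Part II, Informed Consent for Patients: testing needs only the laboratory's consent. Survey consent is separate.
- **Route to the follow-up survey.** Part III, Patient Study Population: patients are invited to a baseline survey after consenting to testing and to a follow-up survey after results. On completing the baseline survey, "participants will be asked to indicate if they would be interested in participating in the follow-up survey and re-contacted".
- **Sample size.** Part II, Patient Study Population: "Based on our power calculations, we estimate that we would need to enroll 18 patients per cluster (360 total"). The calculation, its inputs and any allowance for non-response are not given.
- **Safeguards.** Survey Administration provides individual links, reminders to non-responders, and paper or phone options. Incentives pays \$20 for the baseline and \$30 for the follow-up survey. Data Analysis promises complete-case and imputed results, with an examination of whether data are missing at random.

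**The concern.** A patient can be enrolled, tested and counselled and still contribute nothing to the primary comparison. Read as written, the path to a comprehension answer has three voluntary steps: completing the baseline survey, agreeing to re-contact, and answering the follow-up. The comprehension item is scored against the pharmacist's log and does not need the baseline survey, so the first step need not be a condition for the last.

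Two things are at stake. The first is precision, because the number analysed will be smaller than the number enrolled by an amount the plan does not state. The second is selection. The baseline survey screens literacy with a question about confidence in filling out forms. Patients who find forms difficult may plausibly both skip a voluntary form and misunderstand their result. A patient lost at the first step also lacks the literacy, education and prior-knowledge answers that would make a missing-at-random imputation credible.

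**Working it through.** **The plan's own figure.** 20 pharmacies × 18 patients = 360, which agrees with the stated total. The basis of the 18 cannot be reproduced, because alpha, sidedness, power, effect size, comparison rate, ICC and loss are all unstated.

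**Inputs for illustration.** From the documents: 20 clusters, 18 per cluster, a binary endpoint. Assumed here: 10 clusters per arm, two-sided 5%, 80% power, 60% correct in the comparison arm, ICC 0.01, 0.05 or 0.10, and overall retention of 100%, 80%, 64% or 51%. The last three correspond to one, two or three steps each keeping 80%: 0.8; 0.8² = 0.64; 0.8³ = 0.512.

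**Answers available.**

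| Retention | Per cluster | Total |
|---|---|---|
| 100% | 18 | 360 |
| 80% | 18 × 0.8 = 14.4 | 288 |
| 64% | 18 × 0.64 = 11.5 | 230 |
| 51% | 18 × 0.512 = 9.2 | 184 |

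**Formula.** With m answers per cluster, the design effect is 1 + (m − 1) × ICC, and the effective number per arm is n = 10m / design effect. The detectable difference d solves

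d = (1.96 + 0.842) × √{[0.6 × 0.4 + (0.6 + d)(0.4 − d)] / n}.

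**Worked case, m = 18, ICC 0.05.** Design effect 1 + 17 × 0.05 = 1.85; n = 180 / 1.85 = 97.3. At d = 0.182 the bracket is 0.240 + 0.782 × 0.218 = 0.410, so the right side is 2.802 × √(0.410 / 97.3) = 0.182. The equation balances at 18.2 points.

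**Detectable difference from 60%, in percentage points.**

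| Retention | ICC 0.01 | ICC 0.05 | ICC 0.10 |
|---|---|---|---|
| 100% | 14.8 | 18.2 | 21.5 |
| 80% | 16.1 | 19.2 | 22.2 |
| 64% | 17.6 | 20.3 | 23.1 |
| 51% | 19.3 | 21.6 | 24.1 |

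(At 51% and ICC 0.05, rounding m to 9.2 first gives 21.7.) A pooled-variance formula gives slightly larger values at ICC 0.05, 18.5 at full response and 20.7 at 64%, with a similar rise. Both are normal approximations.

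**Selection, mechanics only (assumed rates).** Let true comprehension be 60% in both arms. If 80% of patients who understood and 60% of those who did not respond in both arms, each arm shows 0.48 / (0.48 + 0.24) = 66.7%: the level is wrong, but the difference is still zero. If that pattern holds only in the testing-only arm and 80% of all patients respond in the MTM arm, the result is 66.7% against 60.0%, a spurious 6.7 points. So selection that is the same in both arms distorts the level; a false difference in this example needs response to differ by arm.

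**The case against.** Several points on the other side stand.

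- **The strict gate is inferred.** A reader might conclude that patients who skip the baseline survey are excluded from the follow-up. No sentence says so. Patients are invited to two surveys, and each participant is to receive a link. The documents describe one route and are silent on any other.
- **The 18 may already allow for loss.** A reader might infer that the trial is underpowered because non-response was forgotten. The calculation is not shown, and whether enrolment means testing consent or survey consent is not defined, so that inference is not supported.
- **Non-response is planned for.** Reminders, paper or phone options, the larger follow-up payment and the imputed analyses all help. They do not fully answer the point: the reminders are described for people already sent a link, and imputation for patients without a baseline survey would rest mainly on pharmacy records and the pharmacist's log, without literacy or education.
- **The baseline survey and the re-contact question have a purpose.** They supply covariates and obtain permission where testing carries no research consent. The issue is only that they stand before the follow-up invitation.
- **Bias between arms is undocumented.** The MTM arm has more pharmacist contact, so a difference in response is plausible, but no response data are given and patient payments do not differ by arm.
- **Three separate 20% losses may be pessimistic.** Someone who has just completed one paid survey may well agree to the next.

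**Conclusion.** The concern holds as a gap in the plan, not as proof of a biased or underpowered trial. The described path can lose the primary outcome and the survey predictors for the same patients, and the sample-size statement does not say how many comprehension answers are expected. The cost in precision is moderate: about one point of detectable difference at 80% retention, and 2.6 to 4.5 points at 51%, smaller where the ICC is larger. These figures rest on assumed retention, ICC and a 60% comparison rate. The possible link between non-response and comprehension matters at least as much, but the documents do not allow its size to be estimated. The finding applies to comprehension; acceptance and refill adherence, also listed under Aim 2, do not depend on the surveys.

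**What to change.** 1. In Part III, Patient Study Population, invite every tested patient to the follow-up survey when results are communicated, whether or not the baseline survey was completed.
2. Seek re-contact permission for both surveys when testing consent is taken, with the right to decline either.
3. Keep comprehension as the first follow-up item, as Table 2 already has it.
4. In Part II, Patient Study Population, define enrolment, state whether 18 is the number enrolled or the number expected to give a comprehension answer, and give the power inputs and assumed response. If 18 answers are needed, enrolment at 80% response is 18 / 0.8 = 22.5, so 23 per pharmacy.
5. Report response at each step by arm and pharmacy.

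Cost: revised consent and survey wording, some additional \$30 payments, and some follow-up answers without baseline survey data. Self-selection will be reduced, not removed, because patients may still decline.

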Pharmacist Study Population. A total of 20 pharmacists working in independent community pharmacy settings in North Carolina who are members of the Community Pharmacist Pharmacogenetics Network (CPPN) will be eligible to participate in the cluster randomized trial. CPPN is a collection of community pharmacists in North Carolina who are currently offering or interested in offering PGx testing. Network members enroll with the understanding that they will be contacted regarding potential research studies. In addition, community pharmacies can be referred by CPPN members or contact the study investigator if interested in participating in the study. If additional recruitment is necessary, study staff will contact pharmacist using contact information provided via a mailing list from the North Carolina Board of Pharmacy. No prior experience with PGx testing is required. Pharmacies interested in participating in the MTM + PGx arm will be asked to confirm that they have obtained APhA training or will/have completed our in-person training module on MTM + PGx and have private space in the pharmacy to deliver MTM. If more than 10 pharmacies capable of offering MTM are interested in serving as a study site, we will randomly assign them to a study arm. For each pharmacy, we will request that a single pharmacist be assigned to the study. All pharmacists must participate in the PGx training session prior to patient enrollment and meet with the study pharmacist/study clinical coordinator to review the study protocol.

Patient Study Population. All patients seen by participating pharmacists will be eligible to participate in the study. Patients must be 18 years or older, able to consent to testing on their own

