- **[Baseline & Follow-up]** Several secondary clinical outcomes will be measured to assess overall impact of PGx testing during the follow-up survey including information-seeking about side effects of new drugs and medication adherence. To assess medication adherence, we will use a combination of survey tools and refill data from the pharmacies. Participants will be asked to complete the validated Beliefs about Medicines Questionnaire (BMQ)¹⁰⁴ and Voils medication adherence scale (<https://sites.duke.edu/corrinevoils/versions-of-scale/>). Higher concerns and lower necessity measured by the BMQ have been associated with poorer medication adherence.^{105,107} Although the MMA scale is generally the more accepted tool for self-reported adherence, the BMQ scores can be used as a covariate to determine reasons for non-adherence (e.g., poor satisfaction). In addition, we will assess the psychological impact of testing using the Multidimensional Impact of Cancer Risk Assessment (MICRA) questionnaire.¹⁰⁸ The total score on anxiety and distress subscales range 0 to 105 with a higher score indicating more distress. No studies have defined a cut-off value for high distress; therefore, we will follow the approach by Bjornslett et al¹⁰⁹, and define high distress as a MICRA score above the mean +1 standard deviation.

Pharmacist Patient Log. We will ask pharmacists to keep track of their interactions with each patient to enable analysis of feasibility of delivery of PGx testing in a pharmacy setting and compare responses between pharmacy and patient surveys (see Appendix 7). In particular, we will ask pharmacists to document reason for each interaction with a patient, time spent addressing interaction, whether by phone or in-person, the test result, time spent following up with patient's provider, whether any drug or dosing adjustments were made based on the test result, and refill data. Pharmacy adherence data will extend 6 months after test results are communicated. Two measures of adherence based on data from the pharmacy will be generated: 1) the proportion of days covered¹¹⁰⁻¹¹² (PDC; # of days with drug on-hand]/[# of days in the specified time interval] (x 100)]; and 2) medication possession ratio (MPR; # of days of

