Survey Data Analysis. Analysis of data collected from surveys will be conducted using a software package such as STATA. We will calculate frequency data and statistical associations for the respondent characteristics. Both univariate and multivariate analyses will be conducted for hypotheses (see below). Because the trial uses a cluster design, the analysis will use logistic mixed effects regressions by including treatments as the fixed effect of interest and clusters as random effect. We will first test if the random effect is significant or not. If not, then we will use regular logistic regression to perform the analysis; if significant, we will continue using mixed effect logistic model. In either case, odds ratios and 95% confidence intervals will be generated to assess strength of associations between treatments and outcomes. A secondary analysis will be performed in which the comprehension outcome is not collapsed into “correctly identifying the presence of any variant versus no variants”, but will include correctly indicating the result for each gene (e.g., slow/fast metabolism vs. average). In this case, a logistic random effects model will also be applied with pharmacist and patient as random effects. If a sufficient number of patients are enrolled per drug, a stratified data analysis by drug will be performed to detect any differences regarding comprehension, adherence, or satisfaction. In addition, the impact of time to treatment will be assessed on patient satisfaction and adherence.

- We hypothesize that patients will have a higher level of comprehension of test results from the MTM plus PGx testing than those receiving testing offered as a stand-alone service.
- We hypothesize that patients overall will be satisfied with PGx testing provided through the community pharmacy and likely to have testing again in this setting
- We hypothesize that patients will find PGx testing beneficial, particularly those who have experienced adverse responses or a poor drug outcome in the past, are taking multiple medications, and are older.
- We hypothesize that patients' increased awareness about their genetic risk to adverse responses will result in improved adherence through assurance about the effectiveness and/or safety of their medications.
- We hypothesize that the additional time required to deliver PGx testing as part of an MTM session may present a barrier to providing PGx testing through this approach.

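### The plan names only logistic models, so satisfaction, adherence and pharmacist time, which are numeric, have no usable model for comparing the arms

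*Combined protocol and SAP*

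**What the plan says.** The Survey Data Analysis paragraph says that "the analysis will use logistic mixed effects regressions by including treatments as the fixed effect of interest and clusters as random effect". The random effect is tested first, and for a non-significant result the plan says: "If not, then we will use regular logistic regression to perform the analysis". The effect measure is then fixed: "In either case, odds ratios and 95% confidence intervals will be generated to assess strength of associations between treatments and outcomes". The only further model named is a logistic random-effects model for gene-by-gene comprehension. The paragraph ties its analyses to a list of hypotheses that covers comprehension, satisfaction, perceived benefit, adherence and the time needed for delivery.

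Part III defines the outcomes. Comprehension, named as the primary outcome, is scored correct or incorrect. On the satisfaction questions: "These questions have scale outcomes and will be treated as continuous variables". Self-reported adherence is a survey scale given at baseline and one month after results. On refill data from the Pharmacist Patient Log: "Two measures of adherence based on data from the pharmacy will be generated", namely the proportion of days covered (PDC) and the medication possession ratio (MPR). The same log records the time spent on each interaction.

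Aim 2 states the primary goal as the difference between the two services in acceptance, comprehension, satisfaction and medication adherence. Pharmacist Study Population adds: "For each pharmacy, we will request that a single pharmacist be assigned to the study".

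**The concern.** A binary logistic model needs a yes/no response. Satisfaction, declared continuous, cannot be its response, so one of the two statements has to give way. The plan does not say which. The other numeric outcomes have the same problem without the explicit contradiction.

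The plan therefore fixes no model, effect measure or threshold for two of the four outcomes in Aim 2's primary goal, or for delivery time, which has its own hypothesis. Those choices would be made by the analyst, possibly after seeing the data. An analyst who stayed with the logistic model would need to choose cut-points and would lose information.

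**Working it through.** **1. Match each outcome to the named model.**

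| Outcome | Source | Form | Cut-off stated | Logistic model fits? |
|---|---|---|---|---|
| Comprehension (primary) | Patient follow-up survey | Correct/incorrect | Not needed | Yes |
| MICRA distress | Patient follow-up survey | Score 0 to 105 | Mean + 1 SD | Yes, as high distress yes/no |
| Satisfaction | Patient follow-up survey | Scale, declared continuous | None | No |
| Self-reported adherence | Patient surveys, baseline and 1 month | Scale score | None | No |
| PDC, MPR | Pharmacist log, 6 months | Ratio of days | None | No |
| Time per patient | Pharmacist log | Time | None | No |

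**2. Settle the scope.** The logistic paragraph is headed as survey analysis, whereas PDC, MPR and time come from the log. If the paragraph covers log data, its model does not fit them. If it does not, they have no model for comparing the arms. The gap exists on either reading.

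**3. Pharmacist surveys.** With one pharmacist per pharmacy, a comparison of one value per pharmacist (such as change from pre- to post-study) has one observation per cluster. Between-pharmacy variance then cannot be separated from residual variance. This does not apply to time per patient, which has many records per pharmacy.

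**4. What a cut would cost, if one were made.** The plan's own size is 20 pharmacies × 18 patients = 360, or 180 per arm if split equally; this agrees with the stated total. The available text gives no effect size, intracluster correlation (ICC) or power, so what follows rests on assumptions: a normal outcome, full follow-up and ICC from 0 to 0.10.

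Without clustering, a cut at quantile q keeps a fraction φ(z_q)² / [q(1−q)] of the information:
- Median: 0.3989² / 0.25 = 0.637 = 2/π.
- 80th percentile: 0.2800² / 0.16 = 0.490.

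Clustering softens the loss, because a median split also lowers the ICC, to (2/π)·arcsin(ICC). The fraction kept is 0.637 × (1 + 17·ICC) / (1 + 17·ICC after the split):

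| ICC | Design effect, continuous | ICC after split | Design effect after split | Information kept |
|---|---|---|---|---|
| 0 | 1.00 | 0 | 1.00 | 64% |
| 0.01 | 1.17 | 0.0064 | 1.11 | 67% |
| 0.05 | 1.85 | 0.0318 | 1.54 | 76% |
| 0.10 | 2.70 | 0.0638 | 2.08 | 82% |

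Simulation agrees in direction and size (10 v 10 pharmacies of 18, an assumed difference of 0.35 SD, t-test on pharmacy means, 6,000 trials per setting). Power for the continuous score against the median split was 82% v 67% at ICC 0.01, 64% v 53% at 0.05 and 48% v 41% at 0.10. A repeat run gave the same to within about one point.

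A normal approximation starts from the difference that has 80% power without clustering: (1.960 + 0.842) × √(2/180) = 0.295 SD. After a median split the proportions are 0.500 and 0.616, and power is 60%. It stays at 59 to 60% up to ICC 0.10 if the design effect is held the same before and after the cut, which overstates the loss when there is clustering.

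**The case against.** The best defence is that the logistic paragraph was written for comprehension. It sits under survey analysis, and the next sentences turn to an uncollapsed comprehension outcome for which a logistic model is again used. Calling satisfaction continuous then shows the intended analysis, and the opening line, "Both univariate and multivariate analyses will be conducted for hypotheses (see below"), leaves room for other models. The satisfaction and adherence hypotheses are not themselves worded as contrasts between arms. Part III introduces adherence among secondary clinical outcomes and allows the Beliefs about Medicines Questionnaire (BMQ) score as a covariate.

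Much of this stands. The primary endpoint is untouched, MICRA has a stated cut-off, and BMQ need not be an outcome. For pharmacist surveys, the fallback already allows regression without a random effect, and those surveys are described mainly as a pre/post reassessment.

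A reader might go further and infer that satisfaction, adherence and time would have to be cut in two and lose power. The documents do not support that. Satisfaction is declared continuous, and no threshold is set for any of the three. The tabulated losses describe a cut that nobody has planned.

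What does not stand is that the intended analysis can be read off the text. The logistic paragraph refers to outcomes in general and to hypotheses beyond comprehension, and Aim 2 does call for an arm comparison of satisfaction and adherence. No linear or other continuous-outcome model, and no mean difference, is named anywhere.

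**Conclusion.** The point holds as a conflict and a gap in specification. For satisfaction, two statements in the plan cannot both be followed. For self-reported adherence, PDC, MPR and time per patient, no arm-comparison model that fits the outcome is named. This conclusion rests on the text alone.

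The cost of dichotomising is conditional. A median split would keep about 64% of the information without clustering, rising to about 82% at an ICC of 0.10, under assumed normality. These figures show why the choice should be made in advance; they are not a forecast for this trial.

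The correction is worth making before the data are analysed. Because the dichotomous comprehension analysis is unaffected, it is not essential to the trial's primary result.

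**What to change.** Rewrite the Survey Data Analysis paragraph so that each outcome has a model and an effect measure:

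- **Binary outcomes** (comprehension, and MICRA high distress as already defined): logistic mixed model with odds ratios.
- **Satisfaction and self-reported adherence:** linear mixed model with a pharmacy random intercept and degrees of freedom suited to 20 clusters, reporting mean differences with 95% confidence intervals. Adjust adherence for its baseline score, which is already collected. BMQ may remain a covariate.
- **PDC and MPR:** a cluster-adjusted model that allows for a bounded or skewed scale, for example a fractional-response model with small-sample cluster correction, reported as a difference in means.
- **Matched controls** (two per participant, matched on drug, age and gender): a separate analysis that reflects the matching and the pharmacy. The two-arm model does not cover it.
- **Time per patient:** the same mixed model on the log scale, reported as a ratio.
- **Pharmacist-survey items, if compared between arms:** pharmacist-level change, without a random effect.

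If any numeric outcome is also to be reported as a proportion, state its cut-off now. The cost is wording in the analysis section only, with no new data, visits or patients.
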